### 8.8.1 Planned Genetic Analysis Sample Collection

The planned genetic analysis sample will be drawn for UGT2B17 and CYP2C19 genotyping and for planned analysis of the association between genetic variants in DNA and drug response. If the IRB/IEC does not approve of the planned analysis of the association between DNA variation and drug response, or if there is a local law or regulation prohibiting the same, data analysis will be limited to UGT2B17 and CYP2C19. Leftover extracted DNA will be stored for FBR if the participant provides documented informed consent for FBR.

Sample collection, storage, and shipment instructions for planned genetic analysis samples will be in the operations/laboratory manual.

## 8.9 Future Biomedical Research Sample Collection

If the participant provides documented informed consent for FBR, the following specimens will be obtained as part of FBR:

- Leftover DNA for future research

## 8.10 Health Economics Medical Resource Utilization and Health Economics

Not applicable.

## 8.11 Visit Requirements

Visit requirements are outlined in [Section 1.3](#). Specific procedure-related details are provided in sections below.

### 8.11.1 Screening

Approximately 28 days before (initial) administration of study intervention, potential participants will be evaluated to determine that they fulfill the entry requirements as set forth in [Section 5](#).

Participants may be rescreened after consultation with the Sponsor. Rescreening should include all screening procedures listed in the SoA, including consent review. Rescreen procedures cannot be conducted the day prior to intervention allocation if there are Day -1 procedures planned per protocol.

### **8.11.2 Treatment Period**

Refer to the SoA ([Section 1.3](#)).

### **8.11.3 Participants Discontinued From Study Intervention Continuing to be Monitored in the Study**

At any point if a participant discontinues from study intervention or the study but continues to be monitored in the study, all study procedures specified in the SoA may be completed at the discretion of the investigator and with Sponsor agreement.

### **8.11.4 Poststudy (Follow-up)**

All participants who received at least one administration of study intervention (including participants who terminate the study early) will return to the CRU approximately 14 days after the last administration of study intervention for poststudy (follow-up) procedures, and to determine if any AE has occurred since the last study visit. If the poststudy visit occurs less than 14 days after administration of study intervention, a subsequent follow-up telephone call should be made at 14 days post administration of study intervention to determine if any AEs have occurred since the poststudy clinic visit.

### **8.11.5 Critical Procedures Based on Study Objectives: Timing of Procedure**

For this study, the blood sample collection for MK-6482 is the critical procedure.

At any postdose time point, the blood sample for MK-6482 needs to be collected as close to the exact time point as possible. All other procedures should be completed as close to the prescribed/scheduled time as possible. Study procedures can be performed before or after the prescribed/scheduled time.

The order of priority can be changed during the study with joint agreement of the investigator and the Sponsor Clinical Director.

Any nonscheduled procedures required for urgent evaluation of safety concerns take precedence over all routine scheduled procedures.

The following variance in procedure collection times will be permitted.

- PK Collection as outlined in [Table 4](#).

Table 4 Postdose Pharmacokinetic (Blood) Collection Windows

PK Collection (relative to dosing)	PK Collection Window (relative to scheduled time for collection)
0 to 2 hour	5 min
>2 to 12 hours	15 min
>12 to 48 hours	1 hour
>48 to 72 hours	2 hours

- Postdose standard safety evaluations: vital signs, ECG, pulse oximetry, and clinical laboratory safety tests
  - Prior to 24-hours postdose may be obtained within 15 minutes of the theoretical sampling time
  - Between 24-hours and 48-hours postdose may be obtained within 1 hour of the theoretical sampling time
  - From 48-hours to 72-hours postdose may be obtained within 2 hours of the theoretical sampling time

#### **8.11.6 Study Design/Dosing/Procedures Modifications Permitted Within Protocol Parameters**

This is a Phase 1 assessment of MK-6482 in humans, and the PK, pharmacodynamic, and safety profiles of the compound are still being elucidated. This protocol is written with some flexibility to accommodate the inherent dynamic nature of Phase 1 clinical studies.

Modifications to clinical or laboratory procedures currently outlined may be required to achieve the scientific goals of the study objectives and/or to ensure appropriate safety monitoring of the study participants.

- Instructions to take study intervention with or without food or drink may also be modified based on newly available data
- Modification of the PK/pharmacodynamic sample processing and shipping details based on newly available data

The PK sampling scheme currently outlined in the protocol may be modified during the study based on newly available PK data (eg, to obtain data closer to the time of peak plasma concentrations). If indicated, these collected samples may also be assayed in an exploratory manner for metabolites and/or pharmacodynamic markers.

Up to an additional 50 mL of blood may be drawn for safety and/or PK analyses. The total blood volume withdrawn from any single participant will not exceed the maximum allowable volume during their participation in the entire study ([Appendix 8](#)).

The timing of procedures for assessment of safety procedures (eg, vital signs, ECG, safety laboratory tests, pulse oximetry, etc) may be modified during the study based on newly available data. Additional safety laboratory tests may be added to blood samples previously

drawn to obtain additional safety information. These changes will not increase the number of study procedures for a given participant during their participation in the entire study.

It is understood that the current study may use some or none of the alterations described above. Any alteration made to this protocol to meet the study objectives must be detailed by the Sponsor in a letter to the Study File and forwarded to the investigator for retention. The letter may be forwarded to the IRB/IEC at the discretion of the investigator.

## **9 STATISTICAL ANALYSIS PLAN**

Data will be handled and processed according to Celerion SOPs, which are written based on the principles of GCP.

### **9.1 Statistical Analysis Plan Summary**

This section contains a brief summary of the statistical analyses for this study. Full detail is in the SAP to be provided separately.

Detailed methodology for summary and statistical analyses of the data collected in this study will be documented in an SAP. The SAP will be prepared by Celerion and agreed upon with the Sponsor. This document may modify the plans outlined in the protocol; however, any major modifications of the primary endpoints definition and/or its analysis will also be reflected in a protocol amendment. Additional statistical analyses other than those described in this section may be performed if deemed appropriate.

### **9.2 Responsibility for Analyses**

The statistical analysis of the data obtained from this study will be conducted by the Data Management and Biometrics department at Celerion.

If, after the study has begun, changes are made to the statistical analysis stated below, then these deviations to the plan will be listed, along with an explanation as to why they occurred, in the CSR.

### **9.3 Hypotheses/Estimation**

Primary Estimation:

Estimation: The plasma PK (AUC0-inf and Cmax) of MK-6482 following a single oral 120 mg dose of MK-6482 to participants with ESRD before and after HD will be estimated and compared to each other and to those in healthy matched control participants.

Secondary Estimation:

Estimation: The extent to which MK-6482 is removed by HD from the plasma (eg, CLD, plasma) will be estimated.

## 9.4 Analysis Endpoints

The primary PK endpoints will be AUC0-inf and Cmax of MK-6482 following a single oral dose of MK-6482 to participants with ESRD before and after HD to each other and to those in healthy matched control participants.

Additional PK endpoints will include AUC0-last, AUC0-24, AUC%extrap, Cmax, C24, Tmax, apparent terminal  $t_{1/2}$ ,  $\lambda_z$ , CL/F, and Vz/F.

For ESRD participants in Period 2, the secondary PK endpoint for plasma MK-6482 will include CLDplasma. Additional PK endpoints for ESRD participants in Period 2 will include Ca, Cv, AUC(2-6)Ca, and AUC(2-6)Cv.

## 9.5 Analysis Populations

The following populations are defined for the analysis and reporting of data. All participants will be reported, and their data analyzed, according to the study intervention(s) they actually received.

*All Participants as Treated (APaT):* The All Participants as Treated Population consists of all participants who received at least one dose of study intervention. This population will be used for assessments of safety and tolerability.

*Per-Protocol (PP):* The Per-Protocol Population consists of the subset of participants who comply with the protocol sufficiently to ensure that generated data will be likely to exhibit the effects of treatment, according to the underlying scientific model. Compliance covers such considerations as exposure to treatment, availability of measurements and absence of important protocol deviations. Important protocol deviations will be identified to the extent possible prior to unblinding by individuals responsible for data collection/compliance, and its analysis and interpretation. Any participants or data values excluded from analysis will be identified, along with their reason for exclusion, in the CSR. At the end of the study, all participants who are compliant with the study procedure as aforementioned and have available data considered sufficient to exhibit the effect of treatment will be included in the Per-Protocol dataset. This population will be used for the PK analyses.

## 9.6 Statistical Methods

### 9.6.1 PK Descriptive Statistics

Individual values will be listed for each plasma PK parameter by group and analyte, and the following (non-model-based) descriptive statistics will be provided: N (number of participants with non-missing data), arithmetic mean, standard deviation, arithmetic percent CV (calculated as 100 x standard deviation/ arithmetic mean), median, minimum, maximum, geometric mean, and geometric percent CV (calculated as 100 x sqrt(exp(s) – 1), where s is the observed variance on the natural log-scale.

## 9.6.2 Renal Function Assessment

The following renal function parameters will be calculated for each participant.

### 1. BSA normalized eGFR

The MDRD (Modification of Diet in Renal Disease) equation will be used to estimate GFR standardized to a BSA of 1.73 m^2:

$$\text{eGFR (mL/min/1.73m}^2\text{)} = 175 \times \text{standardized serum creatinine (mg/dL)}^{-1.154} \times \text{age}^{-0.203} \times (0.742 \text{ if female}) \times (1.212 \text{ if Black or African American}).$$

### 2. BSA un-normalized eGFR

The MDRD equation provides an estimate of GFR standardized to a BSA of 1.73 m^2, and it is therefore necessary to multiply this estimate by each participant's ratio of BSA/1.73 to determine the participant specific BSA un-normalized GFR:

$$\text{eGFR (mL/min)} = \text{eGFR (mL/min/1.73m}^2\text{)} \times [\text{BSA (m}^2\text{)} / 1.73].$$

The BSA of an individual is calculated using the following equation:

$$\text{BSA (m}^2\text{)} = [\text{weight (kg)}^{0.425} \times \text{height (cm)}^{0.725}] \times 0.007184. \text{ (Dubois and Dubois, 1916, Wang et al., 1992)}$$

Note: The participants categorized into different renal categories based on BSA normalized eGFR may not fall into the same renal categories after re-categorization based on BSA un-normalized eGFR.

### 3. CLcr using the C-G Equation

CLcr will be estimated using the following equation:

$$\text{CLcr} = \{[140 - \text{age(yr)}] \times [\text{body wt (kg)}] \times (0.85 \text{ if female})\} / [72 \times \text{serum creat (mg/dL)}]$$

Note: The participants categorized into different renal categories based on eGFR using MDRD equation may not fall into the same renal categories after re-categorization based on CLcr by C-G equation.

## 9.6.3 PK Statistical Analysis

Separately for each PK parameter, individual values of MK-6482 AUC0-inf, AUC0-24, and Cmax will be natural log-transformed and evaluated with a linear mixed effects model containing a fixed effect for population (participants with ESRD before and after HD, control participants with normal renal function). An unstructured covariance matrix will be used to allow for unequal population variances and to model the correlation between repeated

measures (before and after HD) within each ESRD participant via the REPEATED and SUBJECT statement in SAS PROC MIXED. Kenward and Roger's method will be used to calculate the denominator degrees of freedom for the fixed effect (DDFM=KR). Ninety percent (90%) CIs for the least squares means for each population will be constructed on the natural log scale and will reference the t-distribution. Exponentiating the least-squares means and their corresponding 90% confidence limits will yield estimates for the population geometric means and confidence intervals about the geometric means on the original scale. Sample SAS code is given below:

```
proc mixed data=data;
  class population subject;
  model lnPk = population /ddf=kr;
  repeated population/ subject=subject type=UN;
  lsmeans population /cl alpha=0.10;
  lsmeans population/pdiff alpha=0.10;
  run;
```

To address the primary estimation objective and compare participants with ESRD before and after HD to participants with normal renal function, a two sided 90% CI for the difference in least-squares means (ESRD before HD – normal renal function, ESRD after HD – normal renal function) will be calculated for each PK parameter using the aforementioned model. These confidence limits will be exponentiated to obtain the 90% CI for the ratio of geometric means (ESRD before HD/normal renal function, ESRD after HD/normal renal function) for each PK parameter. The same approach will be used to address the secondary estimation objective. The extent to which MK-6482 is removed from plasma by HD will be evaluated with the difference in means (ESRD before HD – ESRD after HD), the geometric mean ratio (ESRD before HD/ESRD after HD) and their 90% CIs. A sensitivity analysis may be performed without PMs at UGT2B17 or CYP2C19 if applicable as deemed clinically appropriate.

Figures showing summary plasma concentration-time profiles by population for MK-6482 (linear plot with arithmetic mean ( $\pm$ SD) for concentration and semi-log plot with arithmetic mean) will be provided. A table showing summary PK parameter values with GMs (%GCV) by population, will be provided for MK-6482 AUC0-inf, AUC0-24, Cmax, Tmax, and apparent terminal  $t_{1/2}$ . A table showing the GMR (ESRD before HD /normal renal function, ESRD after HD/normal renal function, ESRD before HD/ESRD after HD) and corresponding 90% CI will be provided for PK parameters, AUC0-inf and Cmax.

Individual values will be listed for each PK parameter for MK-6482 (AUC0-inf, AUC0-last, AUC0-24, AUC%extrap ([percentage of AUC0-inf obtained by extrapolation from 24 hours to  $\infty$ ]),  $\lambda_z$  [terminal elimination rate constant], Cmax, Tmax, CL/F, Vz/F,  $\lambda_z$ , apparent terminal  $t_{1/2}$ , CLD, plasma [dialysis clearance based on plasma], Ca [concentration in plasma samples from the pre-dialyzer line during the dialysis period], and Cv [concentration in plasma samples from the post-dialyzer line during the dialysis period]. The following (non-model-based) descriptive statistics will be provided: N (number of participants with

non-missing data), arithmetic mean, standard deviation, arithmetic percent CV (calculated as 100 x standard deviation/ arithmetic mean), median, minimum, maximum, geometric mean, and geometric percent CV (calculated as 100 x sqrt(exp(s) - 1), where s is the observed variance on the natural log-scale). Descriptive statistics may be provided based on UGT2B17 and/or CYP2C19 phenotypes separately.

Individual participant PK parameter values will also be plotted against BSA normalized eGFR and against BSA un-normalized eGFR, using different symbols to identify participants from each population. For this analysis, eGFR may be calculated as the mean of the two values determined at the prestudy (screening) visit. Plots of PK parameters versus CLcr obtained from C-G equation may be provided. Additionally, plots of PK parameter values versus age and BMI may be provided. PK concentration listings for MK-6482 in plasma, including Ca and Cv concentrations, will be provided for each participant; AUC(2-6)Ca (plasma AUC values determined from Ca versus time profile during the dialysis period from 2 hours to 6 hours postdose using 'linear up, log down' calculation method option in WinNonlin), AUC(2-6)Cv (plasma AUC values determined from Cv versus time profile during the dialysis period from 2 hours to 6 hours postdose using 'linear up, log down' calculation method option in WinNonlin) for MK-6482 during HD in Period 2 will be provided for each ESRD participant.

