Renal Function Assessment	X							eGFR will be determined using the MDRD equation. All healthy control participants will also have a measured CLcr as determined by a 24-hour urine collection. This assessment can be done any time prior to Day -1 check-in.
Blood for UGT2B17 Genotyping	X							At least 2 UGT2B17 IM and at least 2 UGT2B17 EM will be enrolled per group.
Blood for CYP2C19 Genotyping	X							
Serum FSH (postmenopausal females only)	X							
HIV, hepatitis B and C screen	X							
Urine/Saliva Drug Screen	X	X						
Urine/Blood/Breathalyzer Alcohol Screen	X	X						
AE/SAE review	X	X	X	X	X	X	X	See Sec. 8.11.4 for poststudy contact details.
Study Intervention Administration								
MK-6482 Administration			X					
Pharmacokinetics								
Blood for Plasma MK-6482 Assay			X	X	X	X		To be collected at predose and at 0.5, 1, 1.5, 2, 3, 4, 5, 6, 9, 12, 24, 36, 48, and 72 hours postdose.
Blood for Protein Binding			X					To be collected at predose.

Study Period in Healthy Control Group							
Study Period:	Screening	Intervention				Poststudy or ET	Notes
Scheduled Day		-1 (C-I)	1	2	3	4	Poststudy (follow-up) will occur approximately 14 days after study intervention administration [ Sec. 8.11.4 ].
Biomarkers							
Blood for Genetic Analysis			X				Collect predose from enrolled participants only [ Sec. 8.8 ].

Abbreviations: AE=adverse event, BMI=body mass index, BP=blood pressure, C-I=check-in, Chem=chemistry, CLcr=creatinine clearance, CYP=cytochrome P450, ECG=electrocardiogram, eGFR=estimated glomerular filtration rate, EM=extensive metabolizer, FBR=future biomedical research, FSH=follicle-stimulating hormone, Hem=hematology, HIV=human immunodeficiency virus, HR=heart rate, IM=intermediate metabolizer, MDRD=Modification of Diet in Renal Disease, RR=respiratory rate, SAE=serious adverse event(s), T=body temperature, UA=urinalysis, UGT=uridine 5'-diphospho-glucuronosyltransferase.

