### 2.1 Study Rationale

The purpose of this study is to determine the impact of markedly impaired renal function on the single-dose PK of MK-6482.

*In vitro*, MK-6482 is a substrate of UGT2B17, CYP2C19 and CYP3A4. Both UGT2B17 and CYP2C19 are polymorphic enzymes and the relative contribution of these 2 enzymes to the elimination of MK-6482 has been elucidated by multiple approaches. The collective results of these analyses indicate that UGT2B17 is the major route of elimination in individuals who express this enzyme, while CYP2C19 is also a relevant clearance pathway. The overall contribution of CYP3A4 to MK-6482 metabolism is anticipated to be minor in individuals with intact UGT2B17 and CYP2C19 enzyme activity. A human ADME study (MK-6482-008) is currently ongoing, and is anticipated to confirm that hepatic metabolism represents a major elimination pathway (>20% of the absorbed drug) for MK-6482.

Renal excretion is not anticipated to represent a major clearance route for MK-6482. However, impaired renal function has been demonstrated to alter drug metabolism and transport pathways in the liver and gut, and these effects are more prominent in patients with severely impaired renal function ([Dreisbach, 2009](#)). As an example, CYP2C19 activity was reported to be reduced by 25% in patients with chronic renal impairment characterized by a GFR <50 mL/min ([Dreisbach, 2009](#)). There are no published reports on the impact of renal impairment on UGT2B17 activity. Furthermore, since nephron-sparing surgery is often the treatment of choice for amenable RCC lesions, VHL-RCC patients may undergo multiple sequential renal surgeries, which can lead to progressive worsening of renal function. In a retrospective analysis of 72 VHL patients with a median follow-up period of 61.5 months, 30% of patients who underwent RCC surgery developed chronic kidney disease while 5% of patients developed ESRD and required HD ([Kwon et al., 2014](#)).

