#### **9.9 Sample Size and Power Calculations**

The sample size selected to evaluate the effect of renal impairment on the PK of MK-6482 was not chosen to satisfy any a priori statistical requirement. This sample size (N=6 per group) has historically been shown to be sufficient for studies of this type and should provide adequate data to support the planned analyses. Nevertheless, estimates of the expected precision of the estimates, based on these sample sizes and the known variability obtained from renal PK studies are presented below.

The precision of the estimated GMRs (ESRD before or after HD / normal renal function) of PK parameters obtained from this study can be assessed by calculating the half-width of the

90% CIs expected for the given sample size and assumed variability. The observed between-participant coefficients of variation were 62.44% (~0.574 standard deviation on the log scale) and 56.29% (~0.525 standard deviation on the log scale) for AUC0-inf from food-effect study (Protocol MK-6482-002) and comparative bioavailability study (Protocol MK-6482-006), respectively. Assuming a sample size of 6 participants per population and observed between-participant SD is 0.574 on the log scale, then the half width of the 90% CI of GMR for MK-6482 AUC0-inf on the log scale will be 0.545. The lower and upper 90% confidence limits for the GMR will be given by OBS/1.72 and OBS\*1.72 for AUC0-inf, where OBS is the observed GMR. Thus, for example, if the observed GMR for AUC0-inf was 1.50, then the approximate 90% CI for the GMR would be [0.87, 2.59].

Similarly, the observed between-participant coefficients of variation were 26.04% (~0.256 SD on the log scale) and 25.25% (~0.249 SD on the log scale) for Cmax from Protocol MK-6482-002 and Protocol MK-6482-006, respectively. Assuming a sample size of 6 participants per population and observed between-participant SD is 0.256 on the log scale, then the half width of the 90% CI of GMR for MK-6482 Cmax on the log scale will be 0.243. The lower and upper 90% confidence limits for the GMR will be given by OBS/1.28 and OBS\*1.28 for Cmax. Thus, for example, if the observed GMR for Cmax was 1.50, then the approximate 90% CI for the GMR would be [1.18, 1.91].

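### The primary PK model leaves out UGT2B17 phenotype, which is known before dosing and constrained by quota; if phenotype affects AUC0-inf, the ESRD/normal 90% CI is wider than it needs to be

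*Combined protocol and SAP*

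**What the plan says.** Section 9.6.3 specifies that AUC0-inf, AUC0-24 and Cmax are log-transformed and "evaluated with a linear mixed effects model containing a fixed effect for population". The sample code agrees: "model lnPk = population /ddf=kr". The covariance is flexible ("An unstructured covariance matrix will be used to allow for unequal population variances"), and the primary output is "a two sided 90% CI for the difference in least-squares means", back-transformed to a GMR.

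UGT2B17 matters elsewhere in the plan:
- Section 2.1 states that "UGT2B17 is the major route of elimination in individuals who express this enzyme".
- The schedules of activities place genotyping at screening in both groups, with the rule "At least 2 UGT2B17 IM and at least 2 UGT2B17 EM will be enrolled per group".
- Sections 4.1 and 5 match controls to the ESRD group on genotype. A poor metabolizer (PM) with ESRD should have a PM control. If none can be found, a seventh, non-PM participant with ESRD is added.

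Genotype enters the analysis in three other places: an optional sensitivity analysis without PMs, optional descriptive statistics by phenotype (both in Section 9.6.3), and an exploratory objective in Section 3. None of these commits to an ESRD/normal GMR adjusted for IM versus EM.

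**The concern.** The design constrains a named determinant of exposure, and the primary analysis then ignores it. With equal IM and EM counts in the two groups, phenotype cancels from the difference in means, but the between-phenotype variance remains in the residual that sets the width of the interval. The unstructured covariance does not help: it lets variances differ between populations but does not take phenotype out of any of them.

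This is an estimation study with 6 participants per group, and the 90% CI is its main inferential result, so lost precision is a real cost. The quotas are also only minimums. The two groups may differ in IM/EM mix, and a population-only model then attributes part of the phenotype effect to renal function.

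**Working it through.** **Inputs.** From Section 9.9: 6 per group; log SD 0.574 for AUC0-inf and 0.256 for Cmax. From Section 9.6.3: two-sided 90% intervals with t-based limits. Assumed: an IM/EM AUC ratio r between 1.0 and 2.0; 3 IM and 3 EM per group (permitted, not required); and 0.574 as the total SD in an evenly mixed population.

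**1. The plan's figure.** For the AUC0-inf inputs above, Section 9.9 gives this result: "then the half width of the 90% CI of GMR for MK-6482 AUC0-inf on the log scale will be 0.545". 1.645 × 0.574 × √(2/6) = 0.545, a factor of 1.72, so it reproduces with the normal quantile. With t on 10 df (1.812) it is 0.601, a factor of 1.82. The comparisons below are t-based.

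**2. Algebra, equal counts.** Between-phenotype variance is sg² = 0.25 × (ln r)², and within-phenotype variance is sw² = 0.574² − sg². The true variance of the group difference is (2/6) × sw². The planned standard error instead uses a sample variance with expectation sw² + 1.2 × sg².

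| r | sg² | sw | √(sw² + 1.2 sg²) | Unadjusted half-width, t(10) = 1.812 | Adjusted half-width, t(9) = 1.833 | Narrower by |
|---|---|---|---|---|---|---|
| 1.5 | 0.0411 | 0.537 | 0.581 | 0.608 | 0.568 | 6.5% |
| 2.0 | 0.1201 | 0.458 | 0.595 | 0.622 | 0.484 | 22% |

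Each half-width is t × SD × √(2/6).

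**3. Simulation, equal counts.** There were 200,000 data sets per case. A Welch interval stands in for the planned unequal-variance model with Kenward-Roger df. The adjusted interval is from a linear model with pooled variance.

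| r | Planned coverage | Adjusted coverage | Mean half-width, planned to adjusted | Narrower by |
|---|---|---|---|---|
| 1.0 | 90.5% | 90.0% | see step 5 | – |
| 1.5 | 92.5% | 90% | 0.603 to 0.552 | about 8% |
| 2.0 | 96.5% | 90% | 0.619 to 0.471 | about 24% |

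Part of the last column comes from pooling the variances; step 2 compares like with like. In the version most costly in df (unequal variances and separate phenotype means in each group), the adjusted half-widths are 0.574 and 0.489, which is 5% and 21% narrower. At r = 1.25 that version gains nothing (0.598 to 0.602).

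**4. Permitted unequal counts.** With 4 IM/2 EM in ESRD and 2 IM/4 EM in controls, the IM share differs by 4/6 − 2/6 = 1/3. The unadjusted GMR is multiplied by r^(1/3), which is 1.14 at r = 1.5 and 1.26 at r = 2.0. On the log scale the first is ln(1.5)/3 = 0.135, under a quarter of a half-width of about 0.60. The shift reverses if the counts are reversed.

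**5. Cost if phenotype has no effect.**
- Balanced counts, pooled variance: 0.607 against 0.601, about 1% wider.
- Balanced counts, unequal variances and group-specific phenotype means: 0.613 against 0.595, about 3% wider.
- Counts of 2/4 v 4/2: variance inflation is 1/(1 − 1/9) = 1.125. √1.125 × 1.833/1.812 = 1.07, so about 7% wider than the pooled interval. It is about 5% wider than the planned unequal-variance interval, which starts slightly wider.

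**6. Cmax.** Total variance is 0.256² = 0.0655. At r = 2.0, sg² would be 0.1201, which exceeds it. The largest possible ratio under the same even-mix assumption is exp(2 × 0.256) = 1.67. The range in steps 2 and 3 therefore does not carry over.

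**The case against.** The strongest reply is that everything depends on an effect the documents do not quantify. Section 2.1 ranks UGT2B17 among elimination routes but gives no IM/EM exposure ratio, and a small difference between IM and EM would make adjustment worthless or slightly harmful. This stands, and it makes the point conditional. A reader might infer that the planned interval is too wide as a matter of fact; the documents support only that it is wider than needed if phenotype matters enough. With two levels, break-even is about 2% of log-scale variance under pooled variance and about 5% in the version most costly in df.

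A reader might also infer that the design fixes the IM/EM mix. It does not: four of six places per group are constrained and two are free. Balanced 3/3 is one permitted outcome.

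Other points stand in part:
- The genotype mix behind the 0.574 figure is not given, so the even-mix anchor is an assumption.
- A PM present in only one group, given its own level, would contribute nothing to the adjusted ESRD/normal contrast.
- Age, BMI and sex are also matched and not adjusted for. With 12 participants not everything can be, but UGT2B17 is the factor the plan itself names as the major elimination route.
- Section 9.1 defers detail to a separate SAP and permits further analyses. The analyses now listed are optional, and dropping PMs does not adjust for IM versus EM.

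**Conclusion.** The point holds in conditional form, for AUC0-inf and the ESRD/normal comparisons. Assuming a 3/3 split in each group, a total log SD of 0.574 and an IM/EM ratio of 1.5 to 2.0, the nominal 90% interval covers about 92.5% to 96.5%. Adjustment narrows it by about 8% to 24%, or about 5% to 21% without pooling variances.

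With equal counts this is conservatism, not bias: the GMR estimate does not change. A reader might take the omission to invalidate the primary result, and the documents do not support that. Bias arises only with unequal counts, by a factor of about 1.14 at ratio 1.5 in the 4/2 v 2/4 case.

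No size can be claimed for Cmax, for which the documents offer no basis for judging the effect. The ESRD before/after HD contrast is largely unaffected, because phenotype is constant within a participant.

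**What to change.** In Section 9.6.3 and the sample code, prespecify a model with UGT2B17 phenotype as an added fixed effect (`model lnPk = population ugt2b17`), keeping the unstructured covariance and Kenward-Roger df. Make it either the primary analysis or a mandatory companion to the population-only model, and settle which before the first control is dosed. Controls are enrolled after the ESRD group, so there is a natural point for this decision; a choice made after seeing the profiles would be post hoc.

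Give any PM its own level. State that a PM present in one group only does not inform the adjusted ESRD/normal contrast, and report the population-only result beside the adjusted one for that reason.

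The change needs SAP wording and one model term, with no new data. It uses 1 df, or 2 if a PM is enrolled. If phenotype has no effect, the price is the wider interval in step 5 of the working: about 1% to 3% with balanced counts and about 5% to 7% with 2/4 v 4/2.
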